## 2.5 Interim Analyses

No interim analysis is planned for the study.

## 2.6 Study Procedure

The physician investigator will perform the spinal needle procedure (to introduce medications or image contrast agents) based on the medical needs of the participant. The physician investigator will choose the vertebral interspace, participant position, procedure/ technique, and BD spinal needles. The participant will be monitored closely at regular intervals per practice guidelines and site policies.

The physician investigator will document the procedure in a standard procedure note. The note should include but is not limited to the equipment/devices used, participant position, interspace level, number of attempts, and any identified complication or adverse event. If used, spinal medications with amounts will also be documented. After the procedure is completed, the physician investigator will complete a short ease of use survey regarding the performance of the devices used. Physician performing procedure experience (years of experience, estimated number of spinal needle procedures performed and the education) data collected through an Inserter Experience Survey: data will be part of the final database; no analysis is planned. The data will be provided as Excel spreadsheet only.

The participant will be acutely monitored as required for their routine medical care and according to site policy. Complications or adverse events (e.g., PDPH) will be monitored for the 7-day period after the procedure. If the participant is discharged from the hospital during this time period, follow-up may be performed in a variety of ways including by telephone.

## 2.7 Endpoints

Refer to Section **Error! Reference source not found..**

## 2.8 Acceptance Criteria

There are no acceptance criteria for the study device.

# 3 Intended Statistical Software and Data Information

## 3.1 Intended Statistical Software

All the analyses will be performed using Statistical Analysis System (SAS) Version 9.4 or above or R.

## 3.2 Data Information

Derived data specification can be found in Appendix 2.

# 4 Analysis Population Set(s)

## 4.1 Population Definitions

**Enrolled:** All participants who sign the ICF.

**Evaluable:** All participants in whom a neuraxial procedure is attempted, regardless of success. It will include the following participants in the Spinal Needle Procedure CRF page:

- Was spinal needle procedure performed: Equals ‘Yes’.

**Safety:** All participants on whom an anesthesia procedure is performed. It will include the following participants in the Spinal Needle Procedure CRF page:

- Was there a spontaneous appearance of cerebrospinal fluid (CSF) emerging from the needle hub: Equals ‘Yes’.

# 5 Statistical Analysis/Calculations

## 5.1 Primary Safety Endpoints

The primary safety endpoint is the incidence of post-dural puncture headache (PDPH) in the 7 days following the anesthesia procedure. It will be computed as the number of participants experiencing the event divided by the total number of patients on whom anesthesia procedure was performed; 95% confidence interval (exact method) will be calculated. The analysis will be performed on the safety population as defined in section 4.1. Subgroup analysis for the primary safety endpoint will also be performed by spinal needle type and gauge if data permits.

The incidence of PDPH will be based on response to the following question in the “Follow-up Assessments” CRF page: “During the required follow-up period, did the subject have a post-dural puncture headache?” Participants experiencing any severity (mild/moderate/severe) of PDPH will contribute to the incidence count in the numerator.

## 5.2 Primary Performance Endpoints

The primary performance endpoint is the incidence of successful needle placement in the subarachnoid space defined as the appearance of cerebrospinal fluid from the spinal needle hub. It will be computed as the number of

participants experiencing the event divided by the total number of subjects with needles attempted; 95% confidence interval (exact method) will be calculated. The analysis will be performed on the evaluable population as defined in section 4.1. Subgroup analysis for the primary performance endpoint will also be performed by spinal needle type and gauge if data permits.

The incidence of successful needle placement will be based on counts of “Yes” response to the following question in the “Spinal Needle Procedure” CRF page: “Was there a spontaneous appearance of cerebrospinal fluid (CSF) emerging from the needle hub?”

### 5.3 Secondary Safety Endpoints

The secondary safety endpoint is the incidence of any needle or procedure-related adverse events (other than PDPH). It includes (but is not limited to) the following events:

- Spinal/epidural hematoma
- Nerve damage (pain or weakness lower extremities)
- Infection (Meningitis, spinal abscess)
- Pain, skin redness, irritation at or near the skin puncture site
- Backache

Subject will be considered as having an event if the subject has the following responses for the three questions on the AE CRF Page listed below:

- Can the adverse event be allocated to one of the pre-defined adverse events according to the safety objectives : Not Equals ‘PDPH’

AND

- Relationship to surgical procedure: Equals 'Likely Related' or 'Related' OR Relationship to spinal needle: Equals 'Likely Related' or 'Related'

The incidence will be computed as the number of participants experiencing at least one of these events divided by the total number of evaluable patients; 95% confidence interval (exact method) will be calculated. The analysis will be performed on the evaluable population as defined in section 4.1. Subgroup analysis for the secondary safety endpoint will also be performed by spinal needle type and gauge if data permits.

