3 OBJECTIVES AND ENDPOINTS

Objectives	Endpoints
Primary Safety	
Spinal Needle: Assess the incidence of post-dural puncture headache (PDPH)	Percentage of participants with a diagnosis of PDPH in the 7 days following the anesthesia procedure
Primary Performance	
Spinal Needle: Assess the incidence of successful needle placement	Percentage of successful needle placement in the subarachnoid space defined as the appearance of cerebrospinal fluid from the spinal needle hub
Secondary	
To assess the incidence of any needle or procedure-related adverse events (other than PDPH)	Incidence of device/procedure-related adverse events including but not limited to: 
 • Spinal/epidural hematoma • Nerve damage (pain or weakness lower extremities) • Infection (Meningitis, spinal abscess) • Pain, skin redness, irritation at or near the skin puncture site • Backache

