9.3 Relationship of Adverse Event to Device(s)/Procedure

Each AE will be assessed for its relationship to the study device or procedure according to the following guidelines.

- A. Assess each AE for its relationship to the device or procedure.
 - Device Related: This category should be restricted to AEs directly attributable to the study device used in the neuraxial access procedure.
 - Procedure: A procedure includes any study-related activity performed during the neuraxial procedure.

B. The following categories shall be used for assigning the certainty of the relatedness.

Relatedness	Description
Not Related	Event is independent of study intervention and/or evidence exists that the event is related to another etiology. There must be an alternative etiology documented by the clinician.
Unlikely Related	Event in which the temporal relationship to study intervention makes a causal relationship improbable (e.g., the event did not occur within a reasonable time of the study device use) and in which underlying disease provides plausible explanations (e.g., the participant's clinical condition other concomitant treatments).
Likely Related	Event in which there is evidence to suggest a causal relationship and the influence of other factors is less likely. The event occurs within a reasonable time after use of the study device and is less likely to be attributed to concurrent disease.
Related	Event in which there is clear evidence to suggest a causal relationship and other possible contributing factors can be ruled out. The event occurs in a plausible time relationship to use of the study device and cannot be explained by concurrent disease.

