## 10 SAP Revision History

Version Number	Rationale for Change	Section or Page Affected	Description of Change
1.0	Original SAP		
1.1	Administrative Change	Page 10	MedDRA version 24.0 is changed to 24.1

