**Table 14.2.17 Secondary Safety Endpoints**

Evaluable Population

Level	% (95% CI)
Device/Procedure Related Adverse Events	n/N (%) (xx.x%, xx.x%)
Spinal/epidural hematoma	n/N (%) (xx.x%, xx.x%)
Nerve damage	n/N (%) (xx.x%, xx.x%)

Backache	n/N (%) (xx.x%, xx.x%)
Infection (Meningitis, spinal abscess)	n/N (%) (xx.x%, xx.x%)
Pain, skin redness, irritation at or near the skin puncture site	n/N (%) (xx.x%, xx.x%)

Note: A patient can experience more than one device related adverse events.

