**Table 14.2.17a Secondary Safety Endpoints –Subjects Using Whitacre Needle**

Evaluable Population

Programing Note: Follow the same format as Table 14.2.17.

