**Table 14.3.1.1 Summary of Adverse Events**

## Evaluable Population

	(N=xxx)	
	By Events	By Subjects
Any Adverse Events	xxx	n (%)
Severity		
Mild	xxx	n (%)
Moderate	xxx	n (%)
Severe	xxx	n (%)
Relationship to Procedure 		
Related	xxx	n (%)
Likely Related	xxx	n (%)
Unlikely Related	xxx	n (%)
Not Related	xxx	n (%)
Relationship to Spinal Needle		
Related	xxx	n (%)
Likely Related	xxx	n (%)
Unlikely Related	xxx	n (%)
Not Related	xxx	n (%)
Relationship to Stylet		
Related	xxx	n (%)
Likely Related	xxx	n (%)
Unlikely Related	xxx	n (%)
Not Related	xxx	n (%)
Relationship to Introducer		
Related	xxx	n (%)
Likely Related	xxx	n (%)
Unlikely Related	xxx	n (%)
Not Related	xxx	n (%)
Relationship to Syringe		
Related	xxx	n (%)
Likely Related	xxx	n (%)
Unlikely Related	xxx	n (%)
Not Related	xxx	n (%)
Any Serious AE (SAE)	xxx	n (%)
Relationship to Procedure 		
Related	xxx	n (%)
Likely Related	xxx	n (%)
Unlikely Related	xxx	n (%)
Not Related	xxx	n (%)
Relationship to Spinal Needle		
Related	xxx	n (%)
Likely Related	xxx	n (%)
Unlikely Related	xxx	n (%)

(N=xxx)		
Not Related	xxx	n (%)
Relationship to Stylet		
Related	xxx	n (%)
Likely Related	xxx	n (%)
Unlikely Related	xxx	n (%)
Not Related	xxx	n (%)
Relationship to Introducer		
Related	xxx	n (%)
Likely Related	xxx	n (%)
Unlikely Related	xxx	n (%)
Not Related	xxx	n (%)
Relationship to Syringe		
Related	xxx	n (%)
Likely Related	xxx	n (%)
Unlikely Related	xxx	n (%)
Not Related	xxx	n (%)
Death	xxx	n (%)
Any ADEs 	xxx	n (%)

 The adverse event eCRF page requests the relationship with the surgical procedure and not with the procedure according to the protocol's definition, by mistake. A query was raised for every adverse event reported by the sites in order to clarify the issue and to update the adverse event page accordingly.

 ADEs are defined as any adverse events related or likely related to the spinal needle device.

For by-subject summaries, subjects are counted in the highest severity or most-related category.

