**Table 14.3.1.5 Subjects with Procedure-Related Adverse Events by Body System and Preferred Term**

Evaluable Population

Body System Preferred Term	(N=xxx)
Any Procedure-related* Adverse Events	xxx
Any Subjects with at least one Procedure-related AE	n (xx.x%)
Blood and Lymphatic Disorders	n (xx.x%)
Anemia	n (xx.x%)
Thrombocytopenia	n (xx.x%)
....	
Cardiac Disorders	n (xx.x%)
Myocardial Infarction	n (xx.x%)

\* The adverse event eCRF page requests the relationship with the surgical procedure and not with the procedure according to the protocol's definition, by mistake. A query was raised for every adverse event reported by the sites in order to clarify the issue and to update the adverse event page accordingly.

Programming note: Related includes related and likely related.  
 Body system organ class and preferred term are sorted alphabetically.

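### Does SAP 5.3 count secondary safety events on the wrong relationship because it names the surgical procedure?

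*SAP*

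**What the plan says.** The secondary objective in Protocol section 3 and SAP 1.2 is the incidence of needle- or procedure-related adverse events other than PDPH. Protocol 9.3 says which procedure is meant: "A procedure includes any study-related activity performed during the neuraxial procedure".

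SAP 5.3 turns this into a rule applied to items on the adverse event CRF page. The event must not be classed as PDPH. It must also be rated likely related or related either to the spinal needle or on the item introduced as "Relationship to surgical procedure: Equals". The denominator is the evaluable population, with an exact 95% confidence interval.

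The shells comment on that item. The footnotes to Tables 14.3.1.1 and 14.3.1.5 say that the eCRF page "requests the relationship with the surgical procedure and not with the procedure according to" the protocol definition, and call this a mistake. They add that each reported adverse event was queried "in order to clarify the issue and to update the adverse event page accordingly".

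Table 14.2.17, which reports the endpoint, has a single note: "A patient can experience more than one device related adverse events". For Tables 14.2.17a and 14.2.17b the instruction is "Follow the same format as Table 14.2.17". Table 14.2.17c has no footnote and 14.2.17d copies its layout. The only change logged in the SAP revision history after version 1.0 is "MedDRA version 24.0 is changed to 24.1".

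**The concern.** One part of the SAP package calls the surgical item an error, and another part uses the same item, without comment, to define a prespecified safety endpoint. A programmer who followed 5.3 word for word on uncorrected data would not be measuring what Protocol 9.3 describes. An event put down to the neuraxial technique, but to neither the needle nor the surgery, would drop out of the numerator; backache and puncture-site pain are plausible cases. For a rare complication, losing one case turns one observed into none observed. In addition, a reader of Table 14.3.1.5 is told about the correction and a reader of Table 14.2.17 is not.

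**Working it through.** The plan states no expected rate or precision for this endpoint, so there is no figure to reproduce. The check compares the rules and then asks how far they could diverge.

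**Step 1: which data does 5.3 read?** It reads answers on the adverse event CRF page. The footnotes say the query on every event was meant to update that same page. If the answers were updated there, the item printed with the surgical label holds the relationship to the neuraxial procedure. The 5.3 rule and the protocol rule are then the same rule, and the difference is 0.

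**Step 2: what if the answers had not been updated?** Code each relationship as 1 for likely related or related, and 0 otherwise. The protocol meaning counts an event if neuraxial = 1 or needle = 1. Literal 5.3 counts it if surgery = 1 or needle = 1. Protocol 9.1.1 and SAP 7 limit collection to events with neuraxial = 1 or needle = 1.

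| Neuraxial | Surgery | Needle | Protocol counts | Literal 5.3 counts | Collected |
|---|---|---|---|---|---|
| 0 | 0 | 0 | no | no | no |
| 0 | 0 | 1 | yes | yes | yes |
| 0 | 1 | 0 | no | yes | no |
| 0 | 1 | 1 | yes | yes | yes |
| 1 | 0 | 0 | yes | no | yes |
| 1 | 0 | 1 | yes | yes | yes |
| 1 | 1 | 0 | yes | yes | yes |
| 1 | 1 | 1 | yes | yes | yes |

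The rules differ in 2 of 8 patterns. The surgery-only pattern lies outside the collection rule. Of the 6 collected patterns only one differs: neuraxial yes, surgery no, needle no. This counts logical cases and says nothing about how often that pattern occurs.

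**Step 3: size per participant.** Assume 150 evaluable, the planned maximum.

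- One participant with only such events lowers the rate by 1/150 = 0.67 percentage points.
- The exact 95% interval for 1/150 is 0.02% to 3.66%.
- For 0/150 the upper limit is 1 - 0.025^(1/150) = 2.43%.

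The shells record 15 enrolled participants who were not treated. If exactly 150 were enrolled, n = 150 - 15 = 135. The corresponding figures are 1/135 = 0.74% (0.02% to 4.06%), and an upper limit of 2.70% for 0/135. The documents do not say how many participants had such events, so no bias can be calculated.

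**Step 4: would a lost event be visible?** The collection rule in Step 2 is the same as the protocol's counting rule. If sites followed it, every participant with a collected non-PDPH event belongs in the numerator. Table 14.3.1.2 tabulates all adverse events with no relatedness filter, and Listing 16.2.7.1 gives the predefined category of each. Listing 16.2.9 shows separate follow-up answers on puncture-site pain, irritation and backache attributed to the neuraxial procedure. A shortfall in Table 14.2.17 could be found from these outputs.

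**The case for a change.** The strongest counter-argument is that the footnotes state an intention. They do not say that each query was answered, nor that the corrected value replaced the one first entered. SAP 5.3 does not name the field or mention the correction, and the revision history shows no logged change to it. The collection rule protects against over-counting only. In a study meant to supply clinical data under EU regulation 2017/745, a safety definition should not have to be reconciled with a table footnote.

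Part of this stands. The label in 5.3 does not match Protocol 9.3, the field is not named there, and the footnote is absent from all five endpoint tables. The rest is weaker. The footnotes and 5.3 point to the same page, and nothing mentions a second field, so a literal reading of 5.3 more naturally uses the updated answer. SAP 3.2 places the derived-data specification in Appendix 2, which is not in the text available, so the whole plan cannot be said to be silent on the mapping. The revision history does not show whether 5.3 was written before the eCRF error was found; a printed item label may have been kept on purpose. The footnote appears where relationship to the procedure is itself the reported item. Repeating it under a combined device-or-procedure row would help a reader but alter no number.

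**Conclusion.** No change follows. The mismatch in wording is real but clerical. The package describes the error and the query made for every event, and 5.3 draws on the page that those queries were to update. On that reading the number of misclassified participants is 0. This assumes that the queries were resolved on that page, which the documents suggest but do not confirm. If they were not, the loss would be confined to one relatedness pattern, at 0.67 percentage points per affected participant with 150 evaluable, and the other tables and listings would reveal it. No count of such participants can be derived. The endpoint is secondary and descriptive, and SAP 2.8 sets no acceptance criteria, so no decision depends on it. An analyst who knows of the eCRF error, as the authors of the shells did, would use the corrected answer without further instruction.

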## 6 Summary of General Study Data

### 6.1 Subject Disposition

The summary of the number of subjects in the enrolled population, evaluable population, safety population, as well as those that completed the study, and withdrew from the study with reason for withdrawal will be provided. Screen Failures will be summarized for each inclusion/exclusion criteria that was not met. Summary table will also be provided by site.

### 6.2 Protocol Deviations

A protocol deviation is defined as an event where the Investigator or site personnel did not conduct the study according to the protocol requirements. Any and all protocol deviations must be documented regardless of whether medically justifiable, Sponsor-approved or taken to protect the subject in an emergency.

Details regarding protocol deviations will be listed for evaluable participants.

### 6.3 Demographics and Baseline Variables

Demographics and baseline characteristics will be summarized with descriptive statistics for evaluable population. Summary statistics for categorical variables will include frequency and percentages, and for continuous variables will include mean, standard deviation (SD), minimum, median, and maximum. Demographic data (age (at signing informed consent), gender, race, body height, body weight, body mass index (BMI)) will be tabulated.

The demographic variables will include:

- Age (at signing informed consent)
- BMI
- Body Weight
- Body Height
- Sex
- Race

### 6.4 Medical/Surgical History

Medical history including surgical history will be tabulated and presented at participant-level for evaluable population. Summary tables will be presented for presence of relevant diseases besides primary diagnosis, targeted surgical history, targeted neurological impairment, and targeted anticoagulant therapy. The primary diagnosis for intervention, the reason for neuraxial procedure as well as the ASA classification will be tabulated.

### 6.5 Study Device Procedure

The data related to study device details and placement are recorded on the “Spinal Needle Procedure” section of eCRF page. The device procedure data will be summarized separately for spinal needle procedure, introducer, needle, and syringe for evaluable population.

### 6.6 Follow-up Visit Summary

Follow-up visit summary and listing will be presented for the evaluable population.

### 6.7 Ease of Use Survey

The results for ease of use survey will be presented separately for introducer, spinal needle, stylet, and syringe for evaluable population. The results of the insertion user questionnaire will be tabulated. For each question, the individual results will be tabulated. Additionally, for all scores, a numerical score will be applied (5 = very easy/strongly agree; 1 = very difficult / strongly disagree) and basic statistics will be additionally presented. Data will be presented on the evaluable set.

### 6.8 Device Deficiency

Device failures, malfunctions or defects will be tabulated and presented on participant level for evaluable population. Details regarding device deficiencies will be listed.

## 7 Safety Analysis

An AE is defined as any untoward medical occurrence, unintended disease or injury, or untoward clinical signs (including abnormal laboratory findings) in participants, users or other persons, whether or not related to study device and whether anticipated or unanticipated (ISO 14155:2020). In this study, AE collection will be limited to

those events judged by the investigator to be related or likely related to the neuraxial procedure and/or the BD Spinal Needles used in the procedure.

An overall summary including the number and percentage of subjects with at least one AE, total number of AEs, total number of SAEs, AEs by relationship to the Device/Index Procedure, and AEs by severity of the event will be summarized for the evaluable population.

AEs will be coded by using the Medical dictionary for regulatory activities version 24.1 (MedDRA). All verbatim terms will be coded to the lowest level term (LLT) and will be classified by primary System Organ Class (SOC) according to the MedDRA thesaurus. AEs will be tabulated by SOC and Preferred Term (PT). The number of entries, as well as the number and rate of affected participants will be reported. Additionally, AEs will be presented by severity.

SAEs and AEs which are related to device (adverse device effects [ADEs]), AEs which are related to procedure, or related to accessories (stylet and introducer) will be presented separately. All AEs will be listed together with start date of AE as well as duration of AE for AEs with complete dates.

